1.2.8 Health-related quality of life

It is conceivable that clinical benefit of the tested combined M7824 and M9241 with RT approach is limited to improvement in QoL measures of treated patients. For example, some of the studies of SBRT listed in [Table 3](#) showed ‘only’ self-reported improvement in pain scores and QoL parameters but no change in traditional efficacy readouts response or survival when compared to historical controls. To evaluate the impact of M7824 and M9241 in combination with RT on patients’ pain scores and treatment-related reported symptoms, scores of symptom subsets of the FACT-Hep ([Appendix C](#)) will be longitudinally completed before and during the treatment.

The ‘Functional Assessment of Cancer Therapy’ (FACT-G; version 4) with the hepatobiliary and pancreatic specific module (FACT-Hep)’ is a 45-item self-report instrument developed specifically to measure HRQoL in patients with hepatobiliary cancer (i.e. liver, bile duct and pancreatic cancers; please see ([Appendix C](#))).^[69] It consists of the FACT-G, which assesses symptoms and other HRQoL concerns across four dimensions (physical well-being [PWB; seven items], social/family well-being [SWB; seven items], emotional well-being [EWB; six items] and functional well-being [FWB; seven items]) together with an 18-item disease-specific hepatobiliary cancer subscale (HCS; on page 3 of the instrument) including back and stomach pain, gastrointestinal symptoms, anorexia, weight loss and jaundice in patients with hepatobiliary cancers. It was developed by a process of item generation based on input from patients with hepatobiliary cancers, item reduction based on clinician input, scale construction and reliability/validity testing. Respondents of FACT-based questionnaires rate each item using a five-point Likert-type scale ranging from 0 (not at all) to 4 (very much). The FACT-Hep questionnaire has been shown to be a reliable instrument that correlates with clinical indicators of disease progression and response to treatment and can aid interpretation of HRQL data. Multiple studies in advanced pancreas cancer have reported QoL data in the 2nd and 3rd line setting using the instrument, and measures obtained during this study will be compared to these historical controls.

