⁴ SBRT Radiation therapy on Day 17 (+5 days) of Cycle 1 and continue for 5 consecutive business days (except federal holidays). It will be administered as short course (SBRT) of 5 fractions according to schedule assigned by radiation oncologist.

⁵ Eye signs and symptoms and assessment of skin should be included into physical exam. If clinically indicated, ophthalmology and dermatology consults should be ordered.

⁶ Cycle 1 only, before study treatment.

⁷ Biochemical profile: Acute care panel (that includes sodium, potassium, BUN, creatinine), Hepatic panel (that includes AST, ALT, total bilirubin), Mineral panel (that includes calcium, phosphorus, albumin, magnesium), uric acid

⁸ CT of chest, abdomen and pelvis (or MRI of chest, abdomen and pelvis if clinically indicated). Cycle 3 day 15 (+/- 5 days) and every 2 Cycles (+/-5 days) thereafter. If patient is taken off treatment for reason other than disease progression, imaging evaluations will continue during follow up period every 12 weeks (\pm 2 weeks) until progression. In addition, if PD, a confirmatory scan should be obtained 4 weeks (+ 1 week) following initial documentation of PD.

⁹ Research Quality of Life assessment (subject-reported outcomes / symptom severity assessments the 4th version of the 'Functional Assessment of Cancer Therapy with the hepatobiliary and pancreatic specific module (**Appendix C**)). (For English speaking subjects only. At baseline, cycles 2, 4 and every 12 weeks after that.

¹⁰ At baseline, before treatment on day 1 of cycles 1 and 3 (+/-5 days). Cohort 1A only.

¹¹ See Section **5.1.3**

¹² Before dosing on Cycle 2 day 1

¹³ All subjects should undergo an End-of-Treatment visit after discontinuation of M7824 and M9241 for any reason. This visit should be performed on the day of or within 7 days after the decision to discontinue trial treatment but before any new antineoplastic therapy is started (if possible), whichever occurs earlier. Research samples may be collected as logistically feasible. If it is known to the Investigator at the time of the End of-Treatment visit that the subject will start new treatment within 28 days of last treatment or they will be unable to return within 28 days of last treatment, assessments associated with the 28-Day Safety Follow-up visit may be conducted at the End-of-Treatment visit.

Abbreviated Title: M7824, M9241 and SBRT

Version date: 11/10/2021

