10.4.7 Exploratory analyses

The following are the exploratory objectives, along with the method of analysis of each:

- To determine M7824 PKs. This will be done using descriptive measures only.
- To determine ADA profile of M7824 in combination with M9241. This will be done using descriptive measures only.
- To evaluate serum cytokines and tumor necrosis factor (TNF) levels pre-treatment and on-treatment. These measures will be evaluated using descriptive statistics. Comparisons between pre-treatment and on-treatment levels may be done using a paired test such as a Wilcoxon signed rank test.
- To correlate the tumoral immune infiltrate via IHC with clinical outcome, the levels will be compared between responders and non-responders using an exact Wilcoxon rank sum test.
- To evaluate impact of genomic profile of advanced pancreatic cancers on clinical response to M7824 and M9241 in combination with SBRT. The prevalence of common somatic mutations identified within the 50-cancer gene panel (Molecular Pathology; [name]; for example, KRAS, TP53, SMAD/TGBR2, CDKN2A) obtained from each patient will be compared between responders and non-responders. This will be done using

either a Fisher's exact test, Cochran-Armitage trend test, or exact Wilcoxon rank sum test depending on the distributions of values.

- To correlate circulating free tumor DNA (ctDNA) levels with clinical course of pancreatic cancer patients treated with M7824 and M9241 in combination with SBRT. The levels will be compared between responders and non-responders using an exact Wilcoxon rank sum test.
- To measure subjective Health-related Quality of Life (HRQoL) affecting disease-specific symptoms and treatment-related concerns pre-treatment and on-study and compare HRQoL scores with historical controls of other QoL interventions in advanced pancreas cancer patients. Health-related Quality of Life (HRQoL) scores measuring patient-reported disease-specific symptoms and treatment-related concerns will be compared between responders and non-responders using an exact Wilcoxon rank sum test. The results will also be compared informally with historical controls of other QoL interventions in advanced pancreas cancer patients, using descriptive methods.
- To evaluate the impact of M7824 in combination with M9241 on tumoral perfusion measured by perfusion-weight Dynamic Contrast-enhanced (DCE) Magnetic Resonance Imaging (DCE-MRI). This will be done using descriptive statistics.

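### The only planned HRQoL test compares responders with non-responders, so no planned test can detect an improvement shared by both groups, which is the QoL-only benefit the protocol itself foresees

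*Combined protocol and SAP*

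**What the plan says.** The HRQoL objective, given in Section 1.1.3 and repeated in Section 10.4.7, is to measure HRQoL "pre-treatment and on-study and compare HRQoL scores with historical controls of other QoL interventions in advanced pancreas cancer patients". For the analysis, Section 10.4.7 says that "Health-related Quality of Life (HRQoL) scores measuring patient-reported disease-specific symptoms and treatment-related concerns will be compared between responders and non-responders", by an exact Wilcoxon rank-sum test. It then adds: "The results will also be compared informally with historical controls of other QoL interventions in advanced pancreas cancer patients, using descriptive methods". It does not say which score is used (total or subscale, raw or change), at which time point, or which cohorts enter.

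Section 1.2.8 gives the reason for collecting the data: "It is conceivable that clinical benefit of the tested combined M7824 and M9241 with RT approach is limited to improvement in QoL measures". It points to earlier SBRT series in which patients reported better pain and QoL scores while response and survival did not change. The historical sources it has in mind are studies in advanced pancreas cancer that "have reported QoL data in the 2nd and 3rd line setting".

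Footnote 9 of the Study Calendar (Section 3.8) sets collection as "At baseline, cycles 2, 4 and every 12 weeks after that", for English speakers only. The calendar has no FACT-Hep entry at the end-of-treatment (EOT) visit or the 28-day follow-up visit.

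**The concern.** The stated question is whether HRQoL changes between pre-treatment and on-study, and the rationale singles out the case where it improves without tumor response. The named test asks something else: whether responders score differently from non-responders. That tests an association between response and HRQoL. It carries no information about movement from baseline in the group as a whole.

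The mismatch is worst where the rationale puts the weight. A QoL-only benefit goes with few responders, and with few responders a two-group test is weak or impossible. The same section offers a paired signed-rank test for pre- v on-treatment cytokine levels but nothing comparable for FACT-Hep, although baseline and repeated scores are collected. If the text stays as it is, the time point, scale and method for the pre/on-study contrast would be chosen after the data are seen.

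**Working it through.** **Inputs from Section 10.2.** The phase II design has p0 = 0.10 and p1 = 0.30, 16 evaluable patients at stage 1 (stop at 0 to 1 responses), then 25 in total (success at 5 or more). No power, alpha or effect size is given for HRQoL. The figures below use this phase II set. English-only collection and missing forms can only reduce these numbers. Adding Cohort 1, which the text neither includes nor excludes, would change them.

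**1. The plan's own figure.**
- P(0 of 16) = 0.9^16 = 0.185
- P(1 of 16) = 16 × 0.1 × 0.9^15 = 0.329
- P(0 or 1 of 16) = 0.515 after rounding the exact 0.5147, which matches the stated 51.5%

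**2. Effect of a shared shift on the planned test.** The rank-sum statistic depends only on the ranks. If every patient's score rises by the same amount d, all ranks, and therefore the p-value, stay the same. This is true for raw on-study scores and for change scores. Simulation (4,000 runs per setting, normal scores, two-sided 0.05) gives these rejection rates:

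| Responders v non-responders | d = 0 | 0.3 SD | 0.5 SD | 0.8 SD |
|---|---|---|---|---|
| 5 v 20 | 3.7% | 4.3% | 3.5% | 3.7% |
| 2 v 23 | 4.2% | 4.3% | 3.6% | 4.1% |
| 1 v 15 | 0% | 0% | 0% | 0% |

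The differences along a row are simulation noise.

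**3. Few responders.** The smallest attainable two-sided exact p with R responders among N is 2 / C(N, R).
- R = 0: no comparison exists. The probability at stage 1 is 18.5% if the response rate is 10%.
- R = 1, N = 16: 2/16 = 0.125, so 0.05 is out of reach. The probability is 32.9%.
- R = 2, N = 16: 2/120 = 0.017, so 0.05 becomes attainable.

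Thus 51.5% is the probability, under the null rate, of ending stage 1 with a test that either does not exist or cannot reach 0.05. Only the 18.5% part is the case of no comparison at all.

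**4. A paired analysis of the same patients.** This uses the same simulation and applies a signed-rank test to change from baseline. Normal change scores, two-sided 5% and the SD shifts are assumptions, not figures from the documents.

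| Pairs | 0.3 SD | 0.5 SD | 0.8 SD |
|---|---|---|---|
| 16 | 18% | 44% | 81% |
| 20 | 24% | 54% | 91% |
| 25 | 29% | 64% | 96% |

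The paired test is not strong for small shifts, but its power rises with the effect. The planned test's does not.

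**The case against.** The strongest reply is that the plan does not ignore the foreseen case. Section 10.4.7 adds a comparison with historical controls, and Section 1.2.8 itself frames the QoL-only scenario relative to such controls. HRQoL is exploratory, no decision hangs on it, and nothing stops the investigators from tabulating baseline and on-study scores. A single-arm change from baseline also cannot attribute an improvement to treatment.

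All of this stands and limits the weight of the point. A reader might infer that an improvement without response would go undetected altogether. The documents do not support that, because the historical comparison could show such a signal. It is informal, however, with no named source series, time point or inference.

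A reader might also infer that missing forms and the choice of controls both favour the trial. Neither direction is established:
- Successfully resected patients leave treatment too (Sections 3.5.3 and 3.11.1), so those lost are not only the ones doing badly.
- FACT-Hep is repeated before re-treatment after surgery, and some patients with initial progression stay on treatment until the next scan.
- The Cycle 2 form precedes the first scheduled response scan at Cycle 3 Day 15.
- The calendar does not restrict FACT-Hep by cohort, and Cohort 1 is stage III or IV, for which advanced-disease controls are not plainly mismatched. Cohorts 2 and 3 are locally advanced disease, so for them the difference in stage and line of therapy needs stating.

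Restricting the historical comparison to SBRT series in locally advanced disease is tempting but unsupported. Section 1.2.8 names no instrument for those series, so no FACT-Hep comparator might remain.

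Finally, if only non-responders improved, the rank-sum test could reject. It would then show a difference between groups, not an improvement over baseline.

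**Conclusion.** The point holds as a mismatch between the HRQoL objective and its only test. The insensitivity to a shared improvement is exact and needs no distributional assumption beyond an equal shift in all patients. The small-sample limits are also exact; their probabilities assume a 10% response rate and complete FACT-Hep data in the phase II set. The power of the paired alternative rests on the assumed normal change scores, two-sided 5% level and range of shifts. This goes beyond missing detail, because a better-matched method is available on data already scheduled and is already used elsewhere in the same section. The consequence is confined to an exploratory endpoint; the primary endpoints and the two-stage rule are untouched.

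**What to change.** In Section 10.4.7, make the main HRQoL analysis the within-patient change in FACT-Hep total and in the hepatobiliary subscale, from baseline to Cycle 2 and to Cycle 4, in all patients with data. Report an estimate and confidence interval with a signed-rank test, or use a mixed model with baseline. That is 2 scores × 2 time points = 4 contrasts, to be labelled exploratory. State which cohorts enter and how missing questionnaires are handled. Keep the responder and historical comparisons as descriptive additions, and note the difference in disease stage and line of therapy beside the historical one.

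Optionally, collect FACT-Hep at the existing EOT visit. Scores after discontinuation are otherwise largely missing and may bias later means in a direction that is not established.

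The cost is a few lines of analysis text and, if the EOT form is added, one 20-minute questionnaire at a visit that already takes place. The result would still describe change in a single arm and would not prove a treatment effect.

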11 COLLABORATIVE AGREEMENT

11.1 COOPERATIVE RESEARCH AND DEVELOPMENT AGREEMENT (CRADA)

A CRADA (02666) is in place with EMD Serono for the supply of M7824 and M9241.

12 HUMAN SUBJECTS PROTECTIONS

12.1 RATIONALE FOR SUBJECT SELECTION

No individual who meets the criteria for eligibility will be excluded from participation based on their race, ethnicity, gender, or socioeconomic status. Particular attention will be made to acquire a broad and diversified population.

12.2 PARTICIPATION OF CHILDREN

Individuals under the age of 18 will not be eligible to participate in this study because they are unlikely to have pancreatic cancer, and because of unknown toxicities in pediatric patients.

12.3 PARTICIPATION OF SUBJECTS UNABLE TO GIVE CONSENT

Adults unable to give consent are excluded from enrolling in the protocol. However, re-consent may be necessary and there is a possibility, though unlikely, that subjects could become decisionally impaired. For this reason and because there is a prospect of direct benefit from research participation (Section [12.4.2](#)), all subjects will be offered the opportunity to direct their wishes for research and care to a surrogate, and assign a substitute decision maker on the "NIH Advance Directive for Health Care and Medical Research Participation" form so that another person can make decisions about their medical care in the event that they become incapacitated or cognitively impaired during the course of the study. Note: The PI or AI will contact the NIH Ability to Consent Assessment Team (ACAT) for evaluation to assess ongoing capacity of the subjects and to identify a LAR, as needed.

Please see section [12.5.1](#) for consent procedure.

12.4 RISK/BENEFIT ASSESSMENT FOR ALL PARTICIPANTS

12.4.1 Known Potential Risks

The primary risk to patients participating in this research study is from the toxicity of M7824 and M9241, or from both drugs in combination with SBRT. M7824 and M9241 are investigational agents designed to enhance antitumor efficacy of standard treatment, standard CRT in this protocol. The protocol provides for detailed and careful monitoring of all patients to assess for toxicity.

12.4.1.1 Risk of Rapid Progression

Three large studies of bintrafusp alfa were recently stopped when the drug manufacturer reviewed data that suggested that the studies would not be likely to prove the study treatment better than standard treatments. This data also suggested that there may be a portion of patients that have either no benefit from bintrafusp alfa, or that bintrafusp alfa will make the tumor grow faster. This has been described with other immunotherapy approaches also with studies suggesting this happens in about 15% of cases.

12.4.1.2 Risks of Blood Collection

Risks of blood draws include pain and bruising in the area where the needle is placed, lightheadedness, and rarely, fainting and infection. When large amounts of blood are collected, low red blood cell count (anemia) can develop.

12.4.1.3 Risks of EKG

Risks include some minor skin irritation from the electrodes

12.4.1.4 Risks of exposure to ionizing radiation

Subjects in Cohort 1 in this study may be exposed to radiation from up to 7 CT scans per year for disease assessment (approximately 7.7 rem per year). This amount is more than would be expected from everyday background radiation. Being exposed to excess radiation can increase the risk of cancer. The risk of getting cancer from the radiation exposure in this study is 0.8 out of 100 (0.8%) and of getting a fatal cancer is 0.4 out of 100 (0.4%).

During a year in this research study subjects in Cohort 2 and 3 will be exposed to 25 Gy (5 Gy X 5 days) of radiation from stereotactic body radiation therapy or SBRT. These subjects will also receive a much smaller amount of radiation from up to 7 CT scans for disease assessment. The amount of radiation from these scans adds minimal additional risk to the higher radiation doses received in the course of treatment. This radiation is currently under review by the NIH Radiation Safety Committee.

12.4.1.5 Risks of CT Scans

In addition to the radiation risks discussed above, CT scans may include the risks of an allergic reaction to the contrast. Participants might experience hives, itching, headache, difficulty breathing, increased heart rate and swelling

12.4.1.6 Questionnaires risk

Questionnaires may contain questions that are sensitive in nature. The patients are asked to only answer questions they are comfortable with.

12.4.1.7 Risks of urine collection

There are no risks of urine collection.

12.4.1.8 Risks of MRIs (DCE-MRI)

This study involves MRIs performed for research purposes. The main risk is allergic reaction to IV administered contrast agent. This risk is in the range of 1 to 1.5 %. There is also risk of claustrophobia during MRI and feeling uncomfortable because of loudness of the scanner.

12.4.1.9 Risk of losing data

This includes the risk that data obtained during this study can be released to members of the public, insurers, employers, or law enforcement agencies. Although there are no plans to release results to the patients, family members or health care providers, this risk will be included in the informed consent document

12.4.1.10 Other Risks

Risks include the possible occurrence of any of a range of side effects which are listed in the Consent Document or this protocol document. Frequent monitoring for adverse effects will help to minimize the risks associated with administration of the study agents.

12.4.1.11 Non-Physical Risks of Genetic Research

Risk of receiving unwanted information

Anxiety and stress may arise as a result of the anticipation that unwanted information regarding disease related DNA sequencing or disease tendencies, or misattributed paternity. Patients will be clearly informed that the data related to DNA sequencing and genetic analysis is coded, investigational and will not be shared with patients, family members or health care providers.

Risk related to possibility that information may be released

This includes the risk that data related to genotype, DNA sequencing or risk for disease tendency or trait can be released to members of the public, insurers, employers, or law enforcement agencies. Although there are no plans to release results to the patients, family members or health care providers, this risk will be included in the informed consent document.

12.4.2 Known Potential Benefits

The potential benefit to a patient that goes onto study is a reduction in the bulk of their tumor which may or may not have favorable impact on symptoms and/or survival.

12.4.3 Assessment of Potential Risks and Benefits

For patients with locally advanced pancreas cancer, median overall survival is in the range of 9 months. It is possible that treatment on this protocol may reduce tumor burden, improve resection rates, increase survival, or lessen symptoms caused by the cancer.

Potential adverse reactions attributable to the administration of the study drugs utilized in this trial are discussed in sections **1.2.5.1, 1.2.6.1, 1.2.7**. All care will be taken to minimize side effects, but they can be unpredictable in nature and severity

A number of clinically appropriate strategies to minimize risks to patients have been built into the protocol through the means of inclusion/exclusion criteria, monitoring strategies, and management guidelines. Overall, the potential benefit of the study therapy in subjects with pancreas cancer outweigh the risks associated with study treatment.

12.5 CONSENT PROCESS AND DOCUMENTATION

The informed consent document will be provided as a physical or electronic document to the participant or consent designee(s) (e.g., legally authorized representative [LAR] for re-consent purposes if participant is an adult unable to consent) as applicable for review prior to consenting. A designated study investigator will carefully explain the procedures and tests involved in this study, and the associated risks, discomforts and benefits. In order to minimize potential coercion, as much time as is needed to review the document will be given, including an opportunity to discuss it with friends, family members and/or other advisors, and to ask questions of any designated study investigator. A signed informed consent document will be obtained prior to entry onto the study.

The initial consent process as well as re-consent, when required, may take place in person or remotely (e.g., via telephone or other NIH approved remote platforms used in compliance with policy, including HRPP Policy 303) per discretion of the designated study investigator and with the agreement of the participant/consent designee(s). Whether in person or remote, the privacy of the subject will be maintained. Consenting investigators (and participant/consent designee, when in person) will be located in a private area (e.g., clinic consult room). When consent is conducted remotely, the participant/consent designee will be informed of the private nature of the discussion and will be encouraged to relocate to a more private setting if needed.

Consent will be documented with required signatures on the physical document (which includes the printout of an electronic document sent to participant) or as described below, with a manual (non-electronic) signature on the electronic document. When required, witness signature will be obtained similarly as described for the investigator and participant.

Manual (non-electronic) signature on electronic document:

When a manual signature on an electronic document is used for the documentation of consent at the NIH Clinical Center, this study will use the following to obtain the required signatures:

- Adobe platform (which is not 21 CFR Part 11 compliant); or,
- iMedConsent platform (which is 21 CFR Part 11 compliant).

During the consent process, participants and investigators will view individual copies of the approved consent document on screens at their respective locations if remote consent); the same screen may be used when in the same location but is not required.

Both the investigator and the subject will sign the document using a finger, stylus or mouse.

Note: Refer to the CCR SOP PM-2, Obtaining and Documenting the Informed Consent Process for additional information (e.g., verification of participant identity when obtaining consent remotely) found [here](#).

